5.2. Exploratory Study Arms

The sample size of 20 eligible patients in each of the four exploratory arms was selected because it allows estimation of the CR rate by means of a 90% confidence interval with maximum width of $\pm 18\%$.

6. Treatment Randomization

All patients participating in stage 1 of the primary study or an exploratory study arm will be assigned treatment with ACM. Randomization is not used in these parts of the study.

The remainder of this section refers only to patient participating in stage 2 of the primary study.

Stage 2 of the primary study follows a randomized, two-arm parallel design. The two treatment arms are ACM and CM. Dosages and infusion times are detailed in the study protocol.

Enrolled patients are randomized to receive ACM or CM in a 1:1 ratio and stratified by a three-category classification of response to first-line therapy:

- Refractory – defined as persistent disease or a CR duration less than 90 days
- Early Relapse – defined as a CR duration between 90 days and 1 year
- Late Relapse – defined as a CR duration greater than 1 year but less than 24 months

7. Statistical Methods

Statistical inference (hypothesis testing) to address the first and second objectives shown in section 4.2 will be addressed using data from stage 2 of the primary study only. Data from stage 1 of the primary study and the exploratory study arms will not be used for statistical inference.

Analyses will be performed using SAS statistical software. Default estimation methods in version 9.4 of SAS are always used unless an alternative is specified below. Data summaries will include the mean, standard deviation, median, minimum and maximum values for continuous data; the median, 25th and 75th percentiles, minimum and maximum values for time-to-event endpoints; and the number and percentage of patients in each category for categorical data. Pointwise 95% confidence intervals (CI) will also be estimated for the mean (continuous data), median (time-to-event endpoints) or percentage of patients (categorical data).

In general, data values will be obtained directly from the clinical database (e.g., birth date, treatment dates, AML relapse date and death date). Derivations for certain values not collected explicitly in the database are explained in relevant sections below (e.g., age and treatment failure date, sections 7.7 and 7.9.2, respectively). In some instances, it is beyond the scope of this SAP to explain schemes for patient classifications and data derivations (e.g., classifying patients in cytogenetic risk group according to published criteria). These details will be expounded in the clinical study report.

Durations of time expressed in months (e.g., times-to-event endpoints) will be reported in proportional “months” according to the formula

$$\text{months} = \frac{12}{365.25} \times \text{days}$$

Baseline value of a characteristic is defined as the last measured value prior to the first dose of study drug (or prior to randomization for patients not treated).

Statistical p-values will be truncated for display at the third digit following the decimal point. P-values less than 0.001 will be displayed as “<0.001.”

7.1. Analysis Populations

The intent-to-treat (ITT) patient population includes all patients randomized to receive study drug regardless of whether they actually received study drug and regardless of whether evidence is found indicating they failed to meet study inclusion/exclusion criteria or had other protocol violations. When the ITT patient population is analyzed, patients are grouped according to their randomized treatment regardless of actual treatment received. The ITT patient population is the analysis population for the primary analyses of efficacy endpoints (i.e., all statistical inference and tests of hypotheses related to efficacy endpoints in stage 2 and univariate summaries of efficacy endpoints in stage 1 and the exploratory study arms).

The safety patient population is the subset of ITT patients who received at least one dose of study drug. When the safety patient population is analyzed, patients are grouped according to actual treatment received. ACM is considered a patient’s “treatment received” in the safety patient population if alvocidib is administered at any time during the study (except for ACM administered to a “crossover” patient). The safety patient population is the analysis population for all analyses of safety data.

The response-available patient population is the subset of safety patients who have at least one response assessment on study. However, patients are excluded from the response-available patient population if they have an important protocol deviation, such as when evidence is found indicating they failed to meet any study inclusion/exclusion criterion. When the response-available patient population is analyzed, patients are grouped according to actual treatment received. ACM is considered a patient’s “treatment received” in the response-available patient population if alvocidib is administered at any time prior to a combined remission or at any time during the study for patients never achieving combined remission (except for ACM administered to a “crossover” patient). The response-available population is used for biomarker analyses and sensitivity (secondary, supportive) analyses of efficacy endpoints.

The per-protocol patient population is the subset of safety patients who either (a) have at least one response assessment on study, or (b) die prior to their first scheduled response assessment. However, patients are excluded from the per-protocol patient population if they have an important protocol deviation, such as when evidence is found indicating they failed to meet any study inclusion/exclusion criterion. When the per-protocol patient population is analyzed, patients are grouped according to actual treatment received. ACM is considered a patient's "treatment received" in the per-protocol patient population if alvocidib is administered at any time prior to a combined remission or at any time during the study for patients never achieving combined remission (except for ACM administered to a "crossover" patient). The per-protocol population is used for sensitivity (secondary, supportive) analyses of efficacy endpoints.

The crossover patient population includes all patients randomized to CM who, following 1-2 cycles of CM, receive ACM as stipulated in the study protocol.

Each of the patient populations listed above may be further subdivided for certain analyses. For example, data from ITT patients with relapsed/refractory AML who received ACM (i.e., the ITT population excluding relapsed/refractory patients receiving CM in cycle 1 and patients with newly diagnosed, high-risk AML) will be analyzed to quantify the relationship between baseline MCL-1 dependence and the independent binary variable cycle-1 CR (see section **Error! Reference source not found.**).

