11.3 Analysis Populations

- **Intent-to-treat (ITT) patient population:** includes all patients enrolled into Stage 1; the exploratory arms; or randomized to receive study drug in Stage 2 regardless of whether they actually received study drug and regardless of whether evidence is found indicating they failed to meet study inclusion/exclusion criteria or had other protocol violations. When the ITT patient population is analyzed, Stage 2 patients are grouped according to their randomized treatment regardless of actual treatment received. The ITT patient population is the analysis population for all primary statistical inference and tests of hypotheses related to efficacy endpoints.
- **Safety patient population:** a subset of ITT patients who received at least one dose of study drug. When the safety patient population is analyzed, patients are grouped according to actual treatment received. ACM is considered a patient's "treatment received" in the safety patient population if alvocidib is administered at any time during the study. The safety patient population is the analysis population for all analyses of safety data.
- **Per-protocol patient population:** a subset of the safety patient population who either (a) have at least one response evaluation on study, or (b) die prior to their first scheduled response evaluation. However, patients are excluded from the per-protocol patient population if they have

an important protocol deviation, such as when evidence is found indicating they failed to meet any study inclusion/exclusion criterion. When the per-protocol patient population is analyzed, patients are grouped according to actual treatment received. ACM is considered a patient's "treatment received" in the per-protocol patient population if alvocidib is administered at any time prior to CR (or at any time during the study for patients never achieving CR). The per-protocol population is used for sensitivity (secondary, supportive) analyses of efficacy endpoints.

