PBSC	Peripheral Blood Stem Cells
PFS	Progression-Free Survival
PH	Proportional Hazards (model)

* The term CRp appears in this document to maintain compatibility with the study's case report forms, however CRp will not be used by the hematologists performing the central review of patients' responses and it is not expected to be used by the investigators.

PR	Partial Remission
PT	(MedDRA) Preferred Term
RFS	Relapse-Free Survival
ROC	Receiver Operating Characteristic (curve)
SAE	Serious Adverse Event
SAP	Statistical Analysis Plan
SCT	Stem Cell Transplant/Transplantation
SMQ	Standardized MedDRA Query
SOC	(MedDRA) System Organ Class
TEAE	Treatment Emergent Adverse Event
TLS	Tumor Lysis Syndrome
WHO	World Health Organization

3. Definitions

Standard statistical terminology (e.g., type-1 error rate and significance level) is omitted intentionally. Efficacy endpoints are defined in Section 4.1 below (see Table 1).

Baseline Value: last measured value prior to the first dose of study drug (or prior to randomization for patients not treated)

Combined CR: response assessment of CR, CRi or CRp

Combined Remission: response assessment of CR, CRi, CRp or PR

Crossover Patient: a patient randomized to CM who, following 1-2 cycles of CM, receives ACM as stipulated in the study protocol

Cycle 1: period of time from the first dose of study drug until the start of study drug in cycle 2 or the start of alternative AML therapy other than supportive measures such as blood product transfusions (hence a patient whose first response assessment in cycle 1 is a CRi or CRp is considered to have achieved CR if neutrophils and platelets recover prior to initiation of cycle 2 or alternative AML therapy)

Cycle-1 Combined CR Rate: percentage of patients who achieve a combined CR (CR, CRi or CRp) after one cycle of treatment

Cycle-1 Combined Remission Rate: percentage of patients who achieve a combined remission (CR, CRi, CRp or PR) after one cycle of treatment

Cycle-1 CR Rate: percentage of patients who achieve a CR after one cycle of treatment (see section 7.9.1)

Intent-to-Treat Population: all patients randomized to receive study drug regardless of whether they actually received study drug and regardless of whether evidence is found indicating they failed to meet study inclusion/exclusion criteria or had other protocol violations (see section 7.1)

Neutrophil Recovery: Absolute neutrophil count $\geq 1 \times 10^9/L$ following the administration of study drug

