7.4.1. Outcomes and Study Continuation

Two outcomes are possible from the interim analysis: statistical significance or nonsignificance. In the event of a nonsignificant difference between ACM and CM Cycle-1 CR rates (p-value > 0.00321), the study will continue to accrue and randomize patients.

If the interim analysis result for the primary analysis of Cycle-1 CR rate (see section 7.9.1) is statistically significant (p-value ≤ 0.00321), then randomization will be stopped. Additional eligible stage-2 patients will be enrolled into the study to receive open-label ACM until the planned enrollment of 53 ACM patients is complete. No additional patients will be enrolled into the CM treatment arm. Terminating randomization after the interim analysis will have a negative effect on the power to declare treatment differences in secondary endpoints as statistically significant, however it is understood from polling investigators that they would be unwilling to enroll patients into the study once ACM has been established as superior to CM with respect to Cycle-1 CR rate.

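### The SAP defines ITT as randomised patients and nests the safety, per-protocol and response-available sets inside it, so read literally the non-randomised Stage 1 and exploratory patients belong to no analysis population, against the SAP's own uses and the protocol

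*SAP*

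**What the plan says.** **The SAP definitions**

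- SAP 7.1 on ITT: "The intent-to-treat (ITT) patient population includes all patients randomized to receive study drug regardless of whether they actually received study drug". SAP Section 3 repeats it, and SAP 7.6 equates the number randomised with the ITT population.
- SAP 7.1 on safety: "The safety patient population is the subset of ITT patients who received at least one dose of study drug". It is named as the set for all safety analyses.
- SAP 7.1 on the biomarker set: "The response-available patient population is the subset of safety patients who have at least one response assessment on study". Per-protocol is likewise cut from the safety set, and the crossover set requires randomisation to CM.
- SAP Section 6, on Stage 1 and the exploratory arms: "Randomization is not used in these parts of the study".

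**What the SAP wants from the same patients**

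- SAP 7.1 assigns ITT to the univariate efficacy summaries in Stage 1 and the exploratory arms.
- The closing example in SAP 7.1 takes newly diagnosed patients out of ITT, which presupposes that they were in it.
- SAP 4.2, objective 4, includes a description of safety in newly diagnosed, high-risk AML. Those patients are enrolled only in an exploratory arm.

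**The protocol**

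- Protocol 11.3 says that ITT "includes all patients enrolled into Stage 1; the exploratory arms; or randomized to receive study drug in Stage 2".
- Protocol 4.4.1 keeps Stage 1 drop-outs in the ITT and safety sets.
- Protocol 11.4.4 performs the safety analyses on all patients who receive at least one dose, with no randomisation condition.

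**Inference**

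- SAP Section 7 says that hypothesis testing for objectives 1 and 2 "will be addressed using data from stage 2 of the primary study only".

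**The concern.** The populations form a chain. Randomisation is the entry condition for ITT, ITT for safety, and safety for per-protocol and response-available. A patient who was never randomised fails at the first link and cannot re-enter later. Stage 1 and the four exploratory arms consist entirely of such patients.

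If tables were programmed strictly from SAP 7.1, three things would go wrong:

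- The safety summaries of early mortality, tumor lysis syndrome and serious adverse events would contain no Stage 1 or exploratory patient, and objective 4 would have no data in newly diagnosed AML.
- The biomarker analyses would lose every patient with MCL-1 dependence below 40%. Under the SAP those patients exist only in the exploratory arms.
- The efficacy summaries that SAP 7.1 itself requests for Stage 1 and the exploratory arms would be empty.

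A related gap concerns the time origin. SAP 7.9.4 measures OS from randomisation, and SAP 7.11.1 takes 30- and 60-day mortality from the OS curves. Non-randomised patients have no such date.

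**Working it through.** **1. The SAP's own randomised total.** Inputs from SAP 5.1.2: CR rates of 70% and 40%, one-sided 2.5%, 90% power, a two-stage O'Brien-Fleming design with the interim at 56 of 106 patients, and 1:1 allocation.

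- Information fraction: 56/106 = 0.5283.
- Boundary p-values: 0.00321 and 0.02378, as in SAP Table 3.
- Drift for 90% power: 3.2554.
- Total N = 2 × (3.2554/0.30)² × (0.70 × 0.30 + 0.40 × 0.60) = 2 × 117.75 × 0.45 = 105.97, rounded up to 106.

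The 106 reproduces exactly. These are the only planned patients who meet the SAP's ITT definition.

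**2. Planned patients outside every set.** Inputs from the SAP synopsis: Stage 1 up to 23, four exploratory arms of 20, Stage 2 with 53 per arm. Everyone in Stage 1 and the exploratory arms is assigned ACM.

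- Not randomised: 23 + 4 × 20 = 103.
- All planned patients: 103 + 106 = 209; share outside 103/209 = 49%.
- ACM-assigned: 103 + 53 = 156; share outside 103/156 = 66%.

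**3. The biomarker model.** SAP 7.10 models relapsed/refractory patients receiving ACM.

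- Planned: 23 (Stage 1) + 60 (three exploratory arms below 40% dependence) + 53 (Stage 2 ACM) = 136.
- Left on the literal reading: 53/136 = 39%, all with dependence of at least 40%.

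**4. The texts side by side.**

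- *Stage 1 and exploratory efficacy.* The SAP 7.1 definition excludes these patients. The use that SAP 7.1 assigns to ITT, and protocol 11.3, include them.
- *Stage 1 and exploratory safety.* SAP 7.1 excludes them by nesting. SAP objective 4 includes the newly diagnosed, and protocol 11.3 and 11.4.4 include all who were dosed.
- *Stage 2 ACM-CM tests.* The SAP restricts these to Stage 2 data, and its ITT set is randomised by definition. There is no conflict.

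**5. After the repair.** ITT by the protocol 11.3 wording holds 23 + 80 + 106 = 209 planned patients. The randomised comparison stays at 106 with 90% power.

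**6. Only if the SAP interim is kept.** After a significant interim, SAP 7.4.1 stops randomisation and says: "Additional eligible stage-2 patients will be enrolled into the study to receive open-label ACM until the planned enrollment of 53 ACM patients is complete".

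- Open-label ACM patients: up to 53 − 28 = 25.
- ACM-assigned outside every set: 23 + 80 + 25 = 128 of 156 (82%).

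**The case against.** The strongest reply is that this is loose drafting and nobody would be misled. The sentence in SAP 7.1 on how ITT is used, its closing example and objective 4 all show that the intended ITT set includes Stage 1 and exploratory patients. Protocol 11.3 says so outright, and protocol 11.4.4 covers safety without mentioning randomisation. SAP 7.11.2 also lists all reported adverse events, whatever the summary population. The SAP was written against Amendment 7 and says that later amendments will be reviewed for their effect on it.

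Most of that stands, and it rules out two stronger readings that a reader might infer.

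- *That the safety report will omit most ACM patients.* The documents do not support this as a forecast. The 66% is what the definitions produce when applied literally, against clear signs of the opposite intent. Nor should the SAP wording be applied to the protocol's counts of 25 + 56 = 81 non-randomised patients, because protocol 11.3 puts all 81 in ITT.
- *That open-label ACM patients will enter the randomised comparisons.* As written they would not: ITT is randomised patients grouped by randomised arm. The problem would arise only if ITT were loosened to all enrolled patients while the interim plan was kept, and neither document proposes that. The group itself belongs to the SAP's older design. The current protocol's Study Summary states that there is no interim analysis and plans 28 per arm, so no 53-patient ACM target remains.

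What the reply does not remove is the operative rule. For efficacy, SAP 7.1 at least signals its intent in a parenthesis. It has no equivalent sentence for the safety or response-available sets. SAP Table 9 and the table shells offer no Stage 1 or exploratory column from which the intent could be recovered. Two governing documents therefore define ITT and safety differently.

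**Conclusion.** The SAP's population definitions are wrong as written and conflict with the protocol. Applied literally, they leave 103 of 156 planned ACM-assigned patients (66%) in no population and restrict the biomarker model to 53 of 136 planned patients (39%). These figures are the SAP's planned maxima and count patients by assigned regimen, so CM patients who later cross over to ACM are not included.

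The intent to include the non-randomised patients is evident, so this is an internal contradiction and not a planned exclusion. The primary Stage 2 comparison and its 90% power are untouched. The parts exposed are the safety summaries, the Stage 1 and exploratory efficacy summaries, the biomarker analyses, and the starting date for OS and early mortality in patients without a randomisation date.

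The question of up to 25 open-label ACM patients is conditional on SAP 7.4.1 surviving alignment with the current protocol. If it does, the protocol 11.3 ITT wording would still miss them, although protocol 11.4.4 would reach them for safety.

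**What to change.** Amend SAP Sections 3, 7.1 and 7.6, with matching edits to Table 9 and the table shells, before database lock:

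1. Replace the ITT definition with the protocol 11.3 wording.
2. Define safety as every patient who received at least one dose in any part of the study, in line with protocol 11.4.4. Show Stage 1 and the exploratory arms separately from the randomised arms.
3. State that all ACM-CM hypothesis tests use only patients randomised in Stage 2. This becomes necessary once ITT is wider than the randomised set, and because protocol 11.4 foresees combining Stage 1 with Stage 2 ACM data in secondary analyses.
4. Use the enrollment date as Day 1 for patients who were not randomised, so that OS and 30- and 60-day mortality are defined for them.
5. Only if the SAP 7.4.1 interim plan is retained: place the open-label ACM patients in the safety set as their own group and exclude them from the randomised comparisons.

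The cost is SAP wording and extra table columns. No new data are needed, and neither the sample size nor the primary test changes.

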7.2. Missing Values

In general, missing values will not be replaced by imputed values.

- Although the central hematologists' assessment of response is the primary evaluation, the local assessment (i.e., the one recorded at the study center where the patient is enrolled) will be used for patients who are missing an evaluation from the central hematologists (see section 7.9.1)
- Patients who, for any reason, do not supply bone marrow for response assessment are counted among those not achieving remission
- Patients missing a time-to-event endpoint will have their value censored according to the rules set forth below (see sections 7.9.2 to 7.9.6)

Exceptions to the general rule of not replacing missing values are planned for the following items.

- The first day of the month will be used for a missing day component of a partial birthdate, and January will be substituted for a missing birth month (these substitutions are relevant only for calculating a patient's age)
- Partial start and end dates for adverse events will be replaced by calendar dates that maximize the duration of the adverse event (see section 7.11.2)
- Missing clinical laboratory parameters and vital signs will be replaced using the "last value carried forward" method (see sections 7.11.4 and 7.11.5, respectively)

7.3. Visit Windows

Visit windows are not relevant for analyzing efficacy endpoints since these endpoints are either binary outcomes over the entire study period (e.g., CR rate) or measured on a continuous time scale (e.g., OS and PFS). Some safety assessments (clinical laboratory parameters and vital signs) are summarized over time and visit windows will be used (see sections 7.11.4 and 7.11.5, respectively).

7.4. Interim Analysis

A single interim analysis is planned when cycle-1 response has been defined for 28 patients per treatment arm. Cycle-1 response may be available for more than 28 patients in one treatment arm when the alternate treatment arm reaches 28 because the enrollment ratio may not be precisely 1:1 over time. The additional patients in the faster-enrolling treatment arm will be included in the interim analysis. Therefore, the interim analysis sample size may be slightly more than 56 patients.

Cycle-1 CR rate (the primary efficacy endpoint) will be tested using the statistical procedures described below. As shown in Table 3, a p-value ≤ 0.00321 is required to reject the null hypothesis of equal cycle-1 CR rates across treatment arms.

Measures taken to counter the effect of the interim analysis and maintain an overall 2.5% significance level are presented in section 7.5.1.

